10.8. Interim Analysis

One interim analysis to assess futility will be performed when approximately 30% of the total events (99 deaths) have occurred. A beta-spending function was used to calculate a futility boundary of $Z < -1.9796$ using Gamma (-10) and corresponds to a conditional power level of approximately 18%. Based on the study assumptions, the interim analysis is projected to occur approximately 28 months after the first subject is randomized and at least 60% of subjects have been accrued. At the time of the interim analysis, based on blinded data, the death rate will be evaluated relative to the study assumptions and enrollment into the study may be increased to ensure that the required number of 330 deaths can be reached in approximately 60 months from the time of randomization of the first subject.

[REDACTED]

[Redacted text block]

11. ADVERSE EVENTS

11.1. Monitoring, Recording and Reporting of Adverse Events

An AE is any noxious, unintended, or untoward medical occurrence that may appear or worsen in a subject during the course of a study. It may be a new intercurrent illness, a worsening concomitant illness, an injury, or any concomitant impairment of the subject's health, including laboratory test values (as specified by the criteria below), regardless of etiology. Any worsening (ie, any clinically significant adverse change in the frequency or intensity of a pre-existing condition including AML relapse) should be considered an AE. A diagnosis or syndrome should be recorded on the AE page of the CRF rather than the individual signs or symptoms of the diagnosis or syndrome.

An overdose, accidental or intentional, whether or not it is associated with an AE, or abuse, withdrawal, sensitivity or toxicity to an IP should be reported as an AE. If an overdose is associated with an AE, the overdose and AE should be reported as separate terms.

All subjects will be monitored for AEs during the study. Assessments may include monitoring of any or all of the following parameters: the subject's clinical symptoms, laboratory, pathological, radiological or surgical findings, physical examination findings, or other appropriate tests and procedures.

All AEs will be recorded by the Investigator from the time the subject signs informed consent to 28 days after the last dose of IP or until the last study visit, whichever period is longer. Adverse events and SAEs will be recorded on the AE page of the CRF and in the subject's source documents. All SAEs must be reported to Celgene Drug Safety within 24 hours of the investigator's knowledge of the event by facsimile, or other appropriate method, using the SAE Report Form, or approved equivalent form. Please note that SPMs will be monitored as events of interest throughout the duration of the study including post treatment follow-up period and must be reported as SAEs regardless of the treatment arm the subject is in.

11.2. Evaluation of Adverse Events

A qualified Investigator will evaluate all adverse events as to:

11.2.1. Seriousness

A serious adverse event (SAE) is any AE occurring at any dose that:

- Results in death;
- Is life-threatening (ie, in the opinion of the Investigator, the subject is at immediate risk of death from the AE);
- Requires inpatient hospitalization or prolongation of existing hospitalization (hospitalization is defined as an inpatient admission, regardless of length of stay);
- Results in persistent or significant disability/incapacity (a substantial disruption of the subject's ability to conduct normal life functions);
- Is a congenital anomaly/birth defect;

- Constitutes an important medical event.

Important medical events are defined as those occurrences that may not be immediately life threatening or result in death, hospitalization, or disability, but may jeopardize the subject or require medical or surgical intervention to prevent one of the other outcomes listed above. Medical and scientific judgment should be exercised in deciding whether such an AE should be considered serious.

Second primary malignancies will be monitored as events of interest and must be reported as SAEs regardless of the treatment arm the subject is in (see Section 11.5).

Events **not considered** to be SAEs are hospitalizations for:

- A standard procedure for protocol therapy administration. However, hospitalization or prolonged hospitalization for a complication of therapy administration will be reported as an SAE.
- Routine treatment or monitoring of the studied indication not associated with any deterioration in condition.
- The administration of blood or platelet transfusion as routine treatment of studied indication. However, hospitalization or prolonged hospitalization for a complication of such transfusion remains a reportable SAE.
- A procedure for protocol/disease-related investigations (e.g., surgery, scans, endoscopy, sampling for laboratory tests, bone marrow sampling). However, hospitalization or prolonged hospitalization for a complication of such procedures remains a reportable SAE.
- Hospitalization or prolongation of hospitalization for technical, practical, or social reasons, in absence of an AE.
- A procedure that is planned (ie, planned prior to starting of treatment on study); must be documented in the source document and the CRF. Hospitalization or prolonged hospitalization for a complication remains a reportable SAE.
- An elective treatment of a pre-existing condition unrelated to the studied indication.
- Emergency outpatient treatment or observation that does not result in admission, unless fulfilling other seriousness criteria above.

If an AE is considered serious, both the AE page/screen of the CRF and the SAE Report Form must be completed.

For each SAE, the Investigator will provide information on severity, start and stop dates, relationship to IP, action taken regarding IP, and outcome.

11.2.2. Severity / Intensity

The severity / intensity of AEs will be graded based upon the subject's symptoms according to the currently active minor version of Common Terminology Criteria for Adverse Events (CTCAE, Version 4.0);

http://ctep.cancer.gov/protocolDevelopment/electronic_applications/ctc.htm#ctc_40

AEs that are not defined in the CTCAE should be evaluated for severity according to the following scale:

- Grade 1 = Mild – transient or mild discomfort; no limitation in activity; no medical intervention/therapy required
- Grade 2 = Moderate – mild to moderate limitation in activity, some assistance may be needed; no or minimal medical intervention/therapy required
- Grade 3 = Severe – marked limitation in activity, some assistance usually required; medical intervention/therapy required, hospitalization is possible
- Grade 4 = Life threatening – extreme limitation in activity, significant assistance required; significant medical intervention/therapy required, hospitalization or hospice care probable
- Grade 5 = Death - the event results in death

The term “severe” is often used to describe the intensity of a specific event (as in mild, moderate or severe myocardial infarction); the event itself, however, may be of relatively minor medical significance (such as severe headache). This criterion is *not* the same as “serious” which is based on subject/event *outcome* or *action* criteria associated with events that pose a threat to a subject’s life or functioning.

Seriousness, not severity, serves as a guide for defining regulatory obligations.

11.2.3. Causality

The Investigator must determine the relationship between the administration of IP and the occurrence of an AE/SAE as Not Suspected or Suspected as defined below:

- Not suspected: The temporal relationship of the adverse event to IP administration makes **a causal relationship unlikely or remote**, or other medications, therapeutic interventions, or underlying conditions provide a sufficient explanation for the observed event.
- Suspected: The temporal relationship of the adverse event to IP administration makes **a causal relationship possible**, and other medications, therapeutic interventions, or underlying conditions do not provide a sufficient explanation for the observed event.

If an event is assessed as suspected of being related to a comparator, ancillary or additional IP that has not been manufactured or provided by Celgene, please provide the name of the manufacturer when reporting the event.

11.2.4. Duration

For both AEs and SAEs, the Investigator will provide a record of the start and stop dates of the event.

11.2.5. Action Taken

The Investigator will report the action taken with IP as a result of an AE or SAE, as applicable (e.g., discontinuation or reduction of IP, as appropriate) and report if concomitant and/or additional treatments were given for the event.

11.2.6. Outcome

All SAEs that have not resolved upon discontinuation of the subject's participation in the study must be followed until recovered (return to baseline), recovered with sequelae, or death (due to the SAE).

11.3. Abnormal Laboratory Values

An abnormal laboratory value is considered to be an AE if the abnormality:

- results in discontinuation from the study;
- requires treatment, modification/ interruption of IP dose, or any other therapeutic intervention; or
- is judged to be of significant clinical importance.

Regardless of severity grade, only laboratory abnormalities that fulfill a seriousness criterion need to be documented as a serious adverse event.

If a laboratory abnormality is one component of a diagnosis or syndrome, then only the diagnosis or syndrome should be recorded on the AE page/screen of the CRF. If the abnormality was not a part of a diagnosis or syndrome, then the laboratory abnormality should be recorded as the AE.

11.4. Pregnancy

11.4.1. Females of Childbearing Potential:

Pregnancies and suspected pregnancies (including a positive pregnancy test regardless of age or disease state) of a female subject occurring while the subject is on IP, or within 3 months of the subject's last dose of IP, are considered immediately reportable events. Investigational product is to be discontinued immediately and the subject instructed to return any unused portion of the IP to the investigator. The pregnancy, suspected pregnancy, or positive pregnancy test must be reported to Celgene Drug Safety immediately by facsimile, or other appropriate method, using the Initial Pregnancy Report Form, or approved equivalent form.

The female should be referred to an obstetrician-gynecologist, preferably one experienced in reproductive toxicity for further evaluation and counseling.

The investigator will follow the female subject until completion of the pregnancy and must notify Celgene Drug Safety immediately about the outcome of the pregnancy (either normal or abnormal outcome) using the Follow-up Pregnancy Report Form or approved equivalent form.

If the outcome of the pregnancy was abnormal (eg, spontaneous or therapeutic abortion), the investigator should report the abnormal outcome as an AE. If the abnormal outcome meets any of the serious criteria, it must be reported as an SAE to Celgene Drug Safety by facsimile, or

other appropriate method, within 24 hours of the investigator's knowledge of the event using the SAE Report Form or approved equivalent form.

All neonatal deaths that occur within 28 days of birth should be reported, without regard to causality, as SAEs. In addition, any infant death after 28 days that the investigator suspects is related to the in utero exposure to the IP should also be reported to Celgene Drug Safety by facsimile, or other appropriate method, within 24 hours of the investigator's knowledge of the event using the SAE Report Form, or approved equivalent form.

11.4.2. Male Subjects

If a female partner of a male subject taking IP becomes pregnant while the male subject is on IP, or within 3 months of the male subject's last dose of IP, the male subject taking IP should notify the Investigator, and the pregnant female partner should be advised to call their healthcare provider immediately. Where applicable, the IP may need to be discontinued in the male subject but may be resumed later at the discretion of the Investigator and Medical Monitor.

11.5. Reporting of Serious Adverse Events

Any AE that meets any criterion for an SAE requires the completion of an SAE Report Form in addition to being recorded on the AE page/screen of the CRF. All SAEs must be reported to Celgene Drug Safety within 24 hours of the investigator's knowledge of the event by facsimile, or other appropriate method, using the SAE Report Form, or approved equivalent form. This instruction pertains to initial SAE reports as well as any follow-up reports.

Development of SPMs will be monitored as events of interest throughout the duration of the study including the post treatment follow-up period and must be reported as SAEs regardless of the treatment arm the subject is in. This includes any SPM, regardless of causal relationship to IP (oral azacitidine or placebo), occurring at any time for the duration of the study, from the time of signing the ICD until death, lost to follow-up, withdrawal of consent for further data collection, or study closure. Events of SPM are to be reported using the SAE report form and must be considered an "Important Medical Event" even if no other serious criteria apply; these events must also be documented in the appropriate page(s) of the CRF, ie, AE and SPM and subject's source documents. Documentation on the diagnosis of progression to AML and/or the SPM must be provided at the time of reporting as an SAE (eg, any confirmatory histology or cytology results, X-rays, computed tomography [CT] scans, etc.).

The investigator is required to ensure that the data on these forms are accurate and consistent. This requirement applies to all SAEs (regardless of relationship to IP) that occur during the study (from the time the subject signs informed consent to 28 days after the last dose of IP or until the last study visit, whichever period is longer), and those made known to the investigator at anytime thereafter that are suspected of being related to IP. Serious AEs occurring prior to treatment but after informed consent will be collected.

The SAE report should provide a detailed description of the SAE and include a summary of hospital records and other relevant documents. If a subject died and an autopsy has been performed, copies of the autopsy report and death certificate are to be sent to Celgene Drug Safety as soon as these become available. Any follow-up data will be detailed in a subsequent SAE Report Form, or approved equivalent form, and sent to Celgene Drug Safety.

Where required by local legislation, the Investigator is responsible for informing the Institutional Review Board (IRB)/Ethics Committee (EC) of the SAE and providing them with all relevant initial and follow-up information about the event. The investigator must keep copies of all SAE information on file including correspondence with Celgene and the IRB/EC.

11.5.1. Safety Queries

Queries pertaining to SAEs will be communicated from Celgene Drug Safety to the site via facsimile or electronic mail. The response time is expected to be no more than five (5) business days. Urgent queries (eg, missing causality assessment) may be handled by phone.

11.6. Expedited Reporting of Adverse Events

For the purpose of regulatory reporting, Celgene Drug Safety will determine the expectedness of events suspected of being related to oral azacitidine based on the Azacitidine IB.

For countries within the European Economic Area (EEA), Celgene or its authorized representative will report in an expedited manner to Regulatory Authorities and Ethics Committees concerned, suspected unexpected serious adverse reactions (SUSARs) in accordance with Directive 2001/20/EC and the Detailed Guidance on collection, verification and presentation of adverse reaction reports arising from clinical trials on medicinal products for human use (ENTR/CT3) and also in accordance with country-specific requirements.

Celgene or its authorized representative shall notify the investigator of the following information (in Japan, Celgene KK shall notify the heads of the institutes in addition to the investigators):

- Any AE suspected of being related to the use of IP in this study or in other studies that is both serious and unexpected (ie, SUSAR).
- Any finding from tests in laboratory animals that suggests a significant risk for human subjects including reports of mutagenicity, teratogenicity, or carcinogenicity.
- In Japan, measures taken in foreign countries to ensure subject safety, study reports that indicate potential risk of cancer, etc, or biannual SAE report according to the local regulations.

Where required by local legislation, the investigator shall notify his/her IRB/EC promptly of these new serious and unexpected AE(s) or significant risks to subjects.

The investigator must keep copies of all pertinent safety information on file including correspondence with Celgene and the IRB/EC. (See Section 15.3 for record retention information).

Celgene Drug Safety Contact Information:

For Local Drug Safety Affiliate Office contact information, please refer to the Serious Adverse Event Report Form/Completion Guidelines or to the Pregnancy Report Form/Completion Guidelines.

12. DISCONTINUATIONS

The following events are considered sufficient reasons for discontinuing a subject from the IP / treatment:

- Disease relapse
Subjects will be discontinued from treatment when they meet the following criteria.
 - Appearance of > 15% blasts in the bone marrow or peripheral blood; and
 - The above occurrence should be attributed to relapse following CR/CRi, and not attributable to any other cause (eg, bone marrow regeneration after consolidation therapy or myeloid growth factor administration).
- AE(s)
- Subject withdraws from active treatment but continues follow-up
- Subject becomes eligible (per Investigator) for allogeneic bone marrow or stem cell transplantation during treatment period
- Death
- Lost to follow up
- Protocol violation

Prior to discontinuing IP treatment for a subject assessed to have disease relapse, the Investigator may contact the Medical Monitor and forward appropriate supporting documents for review and discussion.

The reason for discontinuation will be recorded in the CRF and in the source documents.

All subjects discontinued from protocol prescribed treatment for any reason should undergo Treatment Discontinuation procedures including pregnancy test for FCBP. Additionally, all subjects discontinued from protocol prescribed treatment will be followed for a period of 28 days following the last dose of IP or until the date of the last study visit, whichever is later, for the collection of adverse events. Discontinued subjects will not be replaced.

During the follow-up period, all subjects should be followed every month for the first year and then every 3 months thereafter until death for collection of information on survival, AML relapse, monitoring for SPM and subsequent AML therapies, unless the subject has specifically withdrawn consent from further follow-up. Documentation such as laboratory or pathology reports, bone marrow and/or peripheral blood reports supporting the AML relapse will be requested and collected. The Investigator must make every effort to obtain information regarding the subject's survival status before determining the subject is lost to follow-up.

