10.6.1. Primary Efficacy Analysis

The primary efficacy endpoint of OS is defined as the time from randomization to death from any cause and will be calculated using randomization date and date of death, or date of last follow-up for censored subjects. All subjects will be followed until drop-out, death, or study termination. Drop-out may be due to withdrawal of consent from further data collection or loss to follow-up. Subjects who drop-out or are alive at study termination will have their OS times censored at the time of last contact, as appropriate.

The primary efficacy analysis will be conducted for the ITT population and will compare the OS distributions between the two treatment groups. The null hypothesis for testing the primary efficacy endpoint, time to death from any cause, is that the overall survival distributions for the two treatment groups are equivalent. The OS curves will be estimated using Kaplan-Meier (KM) methods. A stratified log-rank test, stratifying by age at time of induction therapy (55-64 years, ≥ 65 years), prior history of MDS (Yes / No), whether consolidation therapy was administered (Yes / No), and cytogenetic risk category at time of induction therapy (intermediate-risk, poor-risk), at a two-sided alpha level of 0.05, will be used to compare the survival distributions between the two treatment groups. The p-value from the stratified log-rank test will be the confirmatory p-value. Kaplan-Meier estimates for median OS as well as the 25th and 75th percentiles and associated two-sided 95% CIs will be summarized for each treatment group, unadjusted for the stratification variables. In addition, both the numerical difference and the 95% CI of the difference, in the median, 25th, and 75th percentiles between the two treatment groups will be presented for the un-stratified analysis. Plots of the KM survival curves will be presented for the two treatment groups, without adjustment for the stratification variables.

A stratified Cox proportional hazards model will be used to estimate the corresponding hazard ratio and 95% CI for azacitidine relative to placebo. Additionally, KM methods will be used to estimate the 1-year and 2-year survival probabilities for time to death from any cause. Estimates of the 1-year (365 days) and 2-year (730 days) survival probabilities and corresponding 95% confidence intervals will be presented by treatment group.

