10.7. Safety Analysis

All safety analyses will be performed on the safety population.

Adverse Events will be coded using MedDRA. Adverse event listings will include the verbatim term and the MedDRA preferred term. Treatment-emergent AEs (TEAEs) will be summarized by worst severity grade, system organ class, and preferred term. Treatment-emergent AEs leading to death or to discontinuation from treatment, AEs classified as CTCAE (Version 4.0) Grade 3 or Grade 4, AEs related to IP, and SAEs will be summarized separately. Time to discontinuation from the study due to AE will be summarized using KM methods. Listings of all deaths and all SAEs, regardless of when they occurred, will also be generated. Development of a SPM will be documented as an SAE (considered to be at least an “important medical event” even if no other seriousness criteria apply) throughout a subject’s duration in the study (signing of ICD through the follow-up period of the study).

Clinical laboratory results will be summarized descriptively by treatment group, which will also include a display of change from baseline. Laboratory values outside of the normal ranges will be identified. Clinically significant hematologic and non-hematologic laboratory abnormalities that meet Grade 3 or Grade 4 criteria according to the CTCAE will be listed and summarized. Graphical display of select laboratory parameters over the course of the study will be provided.

Vital sign measurements and ECOG performance status will be listed for each subject at each visit. Descriptive statistics for the vital signs and ECOG performance status, both observed values and changes from baseline, will be summarized by treatment group.

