## 6. SUBJECT DISPOSITION

All subjects screened/randomized will be included in these analyses. The disposition of subjects will be summarized with counts and percentages. Summaries will include the number of subjects screened and randomized.

For subjects randomized, subject disposition will be summarized for analysis population by treatment arm and overall for:

- ITT Population
- mITT Population
- Safety Population

A listing of reasons for exclusion from the mITT Population will be provided. A separate listing will be provided for subjects not randomized (screen failures) with reasons for screening failure. Listings will be provided for subjects randomized but not treated, and for discontinued subjects with reason for treatment discontinuation.

Reasons for discontinuation from the study treatment phase will be collected on the CRF and will be summarized for all randomized subjects with the following

- Disease relapse
- Adverse event
- Subject withdrew consent
- Physician decision (become eligible for allogeneic bone marrow or stem cell transplantation during treatment period)
- Death
- Subject lost to follow-up
- Protocol violation
- Other

Reasons for discontinuation from the study will be collected on the CRF and will be summarized for all randomized subjects with following:

- Death
- Adverse event
- Pregnancy
- Progressive disease
- Lack of efficacy
- Recovery
- Withdrew consent
- Non-compliance with study drug
- Lost to follow-up
- Study terminated by sponsor
- Transition to commercially available treatment
- Protocol violation
- Other

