## **11.2. Analysis of Primary Efficacy Endpoint**

The primary efficacy variable, time from randomization to death from any cause will be defined as the number of days from the date of randomization until the date of death from any cause, and is calculated by the formula: date of death - date of randomization + 1. Subjects surviving at the end of the follow-up period, or who withdraw consent, or who are lost to follow up will be censored at the date last known alive. For subjects who have withdrawn consent during the study, the last date known alive will be the date of consent withdrawal from the study. For all other subjects, the last date known alive will be derived by searching through all valid assessment dates in all study datasets to identify the last valid subject assessment date available for each subject.

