2. Piecewise cox regression will provide hazard estimates at the following intervals,  $\leq 3$  months,  $3 < \leq 6$  months,  $6 < \leq 12$  months and  $> 12$  months;
3. In the presence of non-proportional and early OS separation, a generalized Wilcoxon test will be utilized to compare survival curves.

To evaluate the impact of censoring in the primary analysis due to subjects who withdrew consent from survival follow-up, a sensitivity analysis of the OS endpoint will be performed. For this analysis, subjects who withdrew consent from survival follow-up will be treated as an event rather than as a censored observation. This sensitivity analysis will be based on the ITT population.

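### The SAP's study-exit codes do not match the survival follow-up rule, and among early OS exits only consent withdrawals get a sensitivity analysis of the treatment effect

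*Protocol*

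**What the plan says.** **The follow-up rule.** Protocol Section 12 sets out reasons for stopping treatment. It then requires survival follow-up, monthly for a year and every three months after that, "until death for collection of information on survival, AML relapse, monitoring for SPM and subsequent AML therapies, unless the subject has specifically withdrawn consent". Protocol 6.14 says the same for stopping therapy for any reason, and adds loss to follow-up and study closure as end points. SAP 4.1.3 repeats the rule. Protocol 10.6.1 defines OS drop-out to match: "Drop-out may be due to withdrawal of consent from further data collection or loss to follow-up".

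**The study-exit list.** SAP 6 first lists reasons for leaving the treatment phase. It then gives a second list: "Reasons for discontinuation from the study will be collected on the CRF and will be summarized for all randomized subjects with following". That list includes adverse event, progressive disease, "Lack of efficacy", non-compliance with study drug and protocol violation. Under the follow-up rule, none of these ends OS follow-up.

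**Wording that blurs the two.** Protocol 10.7 plans: "Time to discontinuation from the study due to AE will be summarized using KM methods". Protocol 11.3 counts a laboratory abnormality as an AE if it "results in discontinuation from the study". Appendix K cites Section 12, which is a list of reasons for stopping treatment, as the source of criteria for leaving the study.

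**OS censoring.** SAP 11.2 names end of follow-up, consent withdrawal and loss to follow-up. It fixes the date for consent withdrawals and continues: "For all other subjects, the last date known alive will be derived by searching through all valid assessment dates". SAP 11.1 plans reverse Kaplan-Meier curves by arm and a table of censoring reasons. In the SAP 11.2.2 analysis of early exits, "subjects who withdrew consent from survival follow-up will be treated as an event rather than as a censored observation".

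**The concern.** The follow-up rule and the study-exit list cannot both describe how a subject leaves survival follow-up. If a site closes a living subject as progressive disease or adverse event and collects nothing further, SAP 11.2 censors that subject at the last valid assessment date. Such censoring is informative, because relapse and serious toxicity both raise the risk of death.

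The descriptive output in SAP 11.1 could show that this happened but would not show what it did to the hazard ratio. The other SAP 11.2.2 analyses deal with subsequent therapy, non-proportional hazards or the mITT population, not with study exit. What is at stake is the primary comparison, if these exits are more common in one arm.

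**Working it through.** **Step 1. Which recorded reasons may end OS follow-up?**

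| Reason in SAP 6 study-exit list | Ends OS follow-up under Protocol 6.14, 10.6.1, 12 and SAP 4.1.3? | In the SAP 11.2.2 early-exit analysis? |
|---|---|---|
| Death | Yes (event) | Not needed |
| Withdrew consent | Yes, if from survival follow-up | Yes |
| Lost to follow-up | Yes | No |
| Study terminated by sponsor | Yes (study end) | Not needed |
| Adverse event, progressive disease, lack of efficacy, non-compliance, protocol violation | No | No |

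The last row is the gap. SAP 15 reports one subject lost to follow-up. No document counts the exits in the last row.

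**Step 2. Reproduce the design figure.** Inputs from Protocol 10.3: hazard ratio 0.70, one-sided alpha 0.025, power 90%, 1:1 allocation. Schoenfeld's formula gives

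D = 4(1.960 + 1.282)² / (ln 0.70)² = 4 × 10.51 / 0.1272 ≈ 330.4, rounded up to 331, against 330 stated.

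Power at 330 deaths is Φ(0.3567 × √330 / 2 − 1.960) = Φ(1.280) = 0.8997. The design reproduces.

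**Step 3. What the 5% drop-out allowance covers.** Let λ = ln 2 / median, with medians 16 and 22.9 months, and η = −ln(0.95)/60. The chance that a death is observed within follow-up f is λ/(λ+η) × [1 − exp(−(λ+η)f)]. Averaging over the stated accrual (25/25/50% over three years) with cut-off at month 60 gives 334.8 expected deaths among 460 subjects, or 339.1 without drop-out. The allowance costs 339.1 − 334.8 = 4.3 deaths. It treats drop-out as unrelated to prognosis and equal in both arms.

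**Step 4. Illustrate exits at relapse.** Assumptions, none from the documents: median 8 months to relapse, then 6 months to death, both exponential; a given share of relapsing subjects is censored at relapse. There are 230 subjects per arm, the stated accrual, cut-off at month 60 and 2,000 runs. HR is the average log-rank estimate exp[(O−E)/V]. The treatment-effect column multiplies both medians by 22.9/16 in the azacitidine arm.

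| Exits, azacitidine / placebo | No effect: HR | One-sided error | Deaths | Treatment effect: HR |
|---|---|---|---|---|
| 0 / 0 | 0.995 | 0.026 | 398 | 0.587 |
| 5% / 5% | 0.995 | 0.029 | 378 | 0.584 |
| 10% / 10% | 0.994 | 0.029 | 358 | 0.582 |
| 5% / 0 | 0.968 | 0.048 | 388 | 0.570 |
| 10% / 0 | 0.940 | 0.081 | 378 | 0.553 |
| 0 / 5% | 1.022 | 0.013 | 388 | 0.601 |
| 0 / 10% | 1.052 | 0.006 | 378 | 0.618 |

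The Monte Carlo standard error at 0.026 is √(0.026 × 0.974 / 2000) ≈ 0.0036, so 0.029 cannot be told apart from 0.026. The rows at 0.048 and 0.081 can.

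**Step 5. A second model.** This one adds a small death hazard in remission (0.003 per month) and varies post-relapse median survival from 4 to 9 months. The relapse hazard is set so that OS medians are 16 and 22.9 months. With 10% of relapsing subjects leaving in both arms, the HR moves 0.005 to 0.017 towards azacitidine and 2-year OS rises by about 1 to 3 points per arm. With 10% leaving in one arm only, the HR moves about 0.015 to 0.045, in a direction set by the arm. The pattern is the same as in Step 4.

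**The case against.** A reader might infer that the plan lets subjects leave survival follow-up at relapse or toxicity. It does not. No passage authorises such an exit, and the follow-up rule is stated consistently in both documents. SAP 6 is a reporting list and looks generic, since it also contains pregnancy and recovery. Protocol 10.7 and 11.3 read most naturally as loose wording for stopping treatment; Protocol 6.6.6 gives the parallel laboratory rule in terms of IP discontinuation. Nothing says that using a study-exit code ends vital-status collection, and SAP 11.2 does not exclude a death recorded after one. All of this stands.

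A reader might also infer that early OS censoring goes unchecked. SAP 11.1 rules that out: it plans reverse Kaplan-Meier by arm and a table of reasons whose examples are open-ended.

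Nor should lost deaths be read as lost power. The trial runs to 330 deaths, so unrecorded deaths mainly delay the cut-off.

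Finally, the exit rates are assumed, and no document shows that exits differ by arm.

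What survives is narrower. The study-exit list stands directly below a treatment list, so loose wording does not explain it. Its codes contradict the follow-up rule, and the checks in SAP 11.1 describe censoring without re-estimating the effect.

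**Conclusion.** The inconsistency is real and touches the primary endpoint. The documents show a reporting list and wording out of step with a clear follow-up rule, together with an early-exit sensitivity analysis limited to consent withdrawals. They do not show that informative censoring occurred.

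The size depends on a count that the documents do not give. Under the assumed models, balanced exits leave the comparison almost unchanged: one-sided error 0.029 against 0.026, and an HR shift of at most 0.017 with 10% leaving. Exits of 5% or 10% of relapsing subjects in the azacitidine arm alone raise the one-sided error to 0.048 or 0.081. The same exits in the placebo arm alone make the test conservative (0.013 or 0.006). Without exits, both models give hazard ratios of about 0.59 to 0.62 rather than the design's 0.70, so only the shifts are informative. The point deserves correction before database lock because the remedy is cheap and the count is knowable.

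**What to change.** 1. Reconcile SAP 6, Protocol 10.7, Protocol 11.3 and Appendix K with the follow-up rule. State that only death, withdrawal of consent to survival follow-up, loss to follow-up or study closure ends OS follow-up. Changing the CRF codes now would not undo data already collected, so steps 2 to 4 matter more.
2. Before database lock, query vital status for every subject closed alive under any other code, and use the result in OS.
3. Present the SAP 11.1 table of censoring reasons by arm, with these codes shown separately.
4. Extend the SAP 11.2.2 analysis from consent withdrawals to all subjects censored alive before the data cut-off because they left the study early.

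The cost is wording changes, one query to sites for the subjects concerned and one small additional analysis. No new patients or procedures are needed. If no such exits exist, the query will show it and step 4 adds only the loss-to-follow-up case.
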